7.3.4. Exploratory Hypotheses:	25
7.4. ADDITIONAL STATISTICAL CONSIDERATIONS	26
7.4.1. Handling of Missing Data	26
7.4.2. Multiplicity	26
7.4.3. Interim Analysis	26
7.4.4. Analysis Sets	26
7.4.5. Pre-specified analysis	26
7.5. DEFINITIONS	26
7.6. RECORDING/REPORTING OF ADVERSE EVENTS	27
7.7. STOPPING RULES.....	28
7.8. MEDICAL MONITORING	28
8. DATA HANDLING AND RECORD KEEPING.....	28
8.1. CONFIDENTIALITY	28
8.2. SOURCE DOCUMENTS	28
8.3. CASE REPORT FORMS	29
8.4. RECORDS RETENTION	30
9. STUDY MONITORING, AUDITING, AND INSPECTING	30
9.1. STUDY SITE MONITORING PLAN	30
10. ETHICAL CONSIDERATIONS.....	31
10.1. CONFLICT OF INTEREST.....	31
11. REFERENCES.....	31

Study Summary

Title	Screening for Peripartum Cardiomyopathies using Artificial Intelligence (SPEC-AI) – Nigeria
Running Title	Screening for cardiac dysfunction in pregnancy
Protocol Number	22-000539
Phase	Other
Methodology	Prospective randomized controlled trial
Overall Study Duration	12 months
Subject Participation Duration	Participation will range from a single encounter/visit to a maximum of 12 months
Single or Multi-Site	Multi-Site
Objectives	To determine the effectiveness of an AI-enabled ECG to detect cardiomyopathy and its impact on clinical outcomes in a predominantly Black obstetric population in Nigeria
Number of Subjects	1,400 enrolled / 1,200 accrued
Diagnosis and Main Inclusion Criteria	
The condition being studied is pregnancy related cardiomyopathy
 
Inclusion Criteria:
 
 • Adult female age of 18 – 49 years • Currently pregnant or within 12 months postpartum • Able to provide consent
Study Product, Dose, Route, Regimen	
Intervention: AI algorithm to evaluate electrocardiogram data and generate prediction probabilities for a diagnosis of cardiomyopathy. To be performed intermittently at pre-specified time points during the study
 
Drug, Dose, Route: Not applicable

Statistical Methodology	The analysis plan will focus on comparing AI-ECG algorithm predictions of low ventricular ejection fraction (<50%) with baseline echocardiograms as the reference criterion (clinical standard) and evaluating the impact of AI-ECG screening on maternal outcomes.

1. Introduction

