**Figure 5. Patient enrollment flow diagram**

[figure not shown]

Figure 6. Study procedures

All patients will have follow-up and medical record review to ascertain the development of study clinical outcomes. Patients can enter the study at any time point (Fig 6) during pregnancy or the postpartum period (up to 12 months after delivery). All women will have a standard 12-lead ECG performed at the time of enrollment and at pre-specified intervals through 12 months postpartum or study end (whichever is earlier). ECGs will be performed up to 7 times during the study period including during each trimester of pregnancy (up to 3 ECGs), post-delivery ECGs may be taken between delivery and 6 weeks (1 ECG), between 6 weeks and 3 months (1 ECG), between 3 and 5 months (1 ECG), and between 5 and 12 months postpartum (1 ECG). Only participants in the intervention arm will have a baseline echocardiogram as well as simultaneous portable ECGs recorded with near real-time provision of AI-ECG cardiomyopathy prediction. Additionally, a newly positive AI-ECG screen for cardiomyopathy during any of the 6 visits will trigger an echocardiogram for participants in the intervention arm. This strategy for performing echocardiograms was selected as it is not practical to obtain an echocardiogram during each prenatal care visit due to time, skilled expertise required, and cost. In addition, the negative predictive value of the AI-enabled ECG is known to be very high (consistently exceeding 95%) in multiple internal and external patient populations (D. Adedinsewo et al., 2020; Attia et al., 2021; Z. I. Attia et al., 2019). Patients in the intervention group with cardiomyopathy detected on an echocardiogram will have a repeat echocardiogram performed at the end of the study period (or at 12 months postpartum depending on which is earlier) as part of the study protocol to assess for left ventricular recovery (Fig 6).

All echocardiograms will be reviewed by the local cardiologists and performed in accordance with American Society of Echocardiography guidelines for ejection fraction assessment as part of the study. LVEF measurements will be recorded for study participants using REDCap.

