3.3. Duration of Participation

An individual participant will be seen ranging from a single visit to a maximum of 7 visits (at pre-specified time points) depending on the time they enter the study (Fig 6). The maximum duration of participation for any one participant is 18 months if they enter the study in the first trimester (after the first 8 weeks to allow room for pregnancy confirmation). In addition, the maximum study duration is estimated to be 18 months due to funding/budgetary restrictions. The minimum duration of participation is one visit (1 day) if they enroll after 9 months postpartum and baseline visit is performed on the same day.

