5.1. Description

Standard ECGs: The study will provide each participating site with a standard 12-lead ECG machine for use for the study as well as standard operating procedures (SOPs) on how to complete and transmit de-identified electronic ECGs to Mayo Clinic with a study identifier attached to each ECG file. Each site will perform a 12-lead ECG during each participant visit using standard clinical protocols. The ECGs recorded will be stripped of personally identifying and study identifier will be attached to the digital 12-lead ECG file. The ECG file will be exported and transmitted to Mayo Clinic study staff in XML format using the secure Mayo Clinic On-Demand File transfer portal. If the stripping of identifiable information should be missed by the site, Mayo Clinic staff will remove the identifying information, and or treat the data as confidential and will keep the file secure in the Mayo Clinic Research Server where only study staff will have access to it.

Echocardiogram: The coordinating center will cover the costs associated with performing echocardiograms per study protocol among study participants randomized to the intervention arm at each site. Results of the echocardiogram will be documented in REDCap. A repeat echocardiogram will be performed if a subsequent AI-ECG result flags positive cardiomyopathy in the intervention arm (if the baseline echocardiogram was normal). The results from the repeat echocardiograms will also be reported in REDCap. All echocardiograms will be reviewed by the local cardiologist at each site and performed in accordance with the American Society of Echocardiography guidelines for ejection fraction assessment.

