6.3. Positive AI-ECG Screen/New Cardiomyopathy Diagnosis (Intervention arm only)

In the event that the AI-ECG detects cardiomyopathy (and baseline echocardiogram showed normal ejection fraction), this would trigger an echocardiogram as part of the research study protocol and the results would be reviewed by a local cardiologist and provided to the managing obstetrician which have already been identified at each site. For participants with newly diagnosed cardiomyopathy (confirmed by echocardiography), the decision to initiate guideline directed medical therapy or other treatment will be based on a clinical evaluation by a local cardiologist at each site, local clinical practice standards, treatment options available and patient preferences.

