7.3. Statistical Hypotheses and planned analyses

7.3.1. Descriptive Statistics

Descriptive statistics including measures of central tendency for numeric variables and frequency distributions for categorical variables will be calculated, as appropriate for all variables. Demographic, clinical, and outcome variables (primary and secondary) will be tabulated for all enrolled study participants. These data will be summarized for the entire cohort and stratified by randomized group and region. We will summarize the measures of diagnostic performance (i.e., AUC, sensitivity, specificity) stratified by study entry to account for the differential follow-up testing that may have occurred as a result of the AI-ECG screening

7.3.2. Primary Hypothesis:

AI-ECG is an effective tool to screen for cardiomyopathy, defined as LVEF < 50%, in pregnant women.

Statistical Hypothesis:

- $H_0: P_{\text{ai-ecg}} = P_{\text{control}}$
- $H_A: P_{\text{ai-ecg}} \neq P_{\text{control}}$

Where P defines the proportion of participants that have documented LVEF <50% by the conclusion of the study.

Primary analysis: A chi-square test without continuity correction will be applied to the resulting two by two table (rows: random treatment assignment, columns LVEF < 50% reported by conclusion of the study). The primary analysis will be conducted at the alpha=0.05 level of significance (two-sided).

7.3.3. Secondary Hypotheses:

AI-ECG will provide consistent performance across race, ethnicity, and postpartum enrollment status.

Secondary analysis: The introduction of stratification factors of race, ethnicity and postpartum status (all unique tables) will be used to produce a stratified contingency table. The Breslow-Day test of homogeneity of the odds ratio will be used to test for effect modification (differential treatment effects by strata). There is the potential for sparse strata with this analysis. If the odds ratio is not estimatable due to zero cells, the empirical logit estimator as well as pooled strata (to increase sample size for each strata) will be utilized.

An AI-ECG is an effective tool to screen for cardiomyopathy at different LVEF cut-off values (<45%, <40%, ≤ 35%).

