Secondary analysis: Within the intervention arm that obtains Echos as a part of the study protocol, the AI-ECG model performance will be evaluated. First, the existing algorithm, without retraining, will be used to evaluate discrimination (area under the receiver operating characteristics curve) at various thresholds for LVEF (i.e., 50% as planned for the primary along with 45%, 40% and 35% as noted here). Performance of the model by the patient stratification factors of Age, Race, Ethnicity, and postpartum status will be considered. For these, the reporting standards outlined in the STARD criteria will be adhered to, e.g., inclusion of measures of precision (confidence intervals) and fractional values associated with measures of performance.

7.3.4. Exploratory Hypotheses:

AI-ECG will improve the diagnosis of cardiovascular disease and associated clinical outcomes among pregnant and postpartum women.

Statistical plan: The analysis of this endpoint will use the same techniques as the primary and secondary analyses. Here, a composite score of any cardiovascular disease diagnoses during the course of the study will be utilized as the outcome measure.

An AI-enhanced point of care screening tool using portable, smartphone-compatible ECG devices (AIPOC-ECG) will be effective for the detection of cardiomyopathies among Black pregnant and postpartum women.

Statistical plan: The primary analysis will utilize the predictions based on the clinical 12 lead ECG machine. This exploratory analysis will compare the model performance on the point of care devices with the clinical standard ECG machine.

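### Sections 7.3.1 and 7.3.3 do not restrict the accuracy analysis to baseline echocardiograms; pooling AI-triggered echoes would bias specificity down, and stratifying by an undefined study entry does not correct it

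*Combined protocol and SAP*

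**What the plan says.** The Study Summary (Statistical Methodology) compares AI-ECG predictions of LVEF below 50% "with baseline echocardiograms as the reference criterion (clinical standard".

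The operative sections differ. Section 7.3.1 summarises AUC, sensitivity and specificity "stratified by study entry to account for the differential follow-up testing that may have occurred as a result of the AI-ECG screening". It names no reference echo and no rule for pairing ECGs with echoes. Section 7.3.3 says: "Within the intervention arm that obtains Echos as a part of the study protocol, the AI-ECG model performance will be evaluated". That set is not limited to baseline.

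The schedule footnote in 6.1.2 gives every intervention-arm woman a baseline echo. Later echoes are selective. Section 3.1 says "a newly positive AI-ECG screen for cardiomyopathy during any of the 6 visits will trigger an echocardiogram for participants in the intervention arm"; section 5.1 says "A repeat echocardiogram will be performed if a subsequent AI-ECG result flags positive cardiomyopathy in the intervention arm", provided the baseline echo was normal; section 6.3 says "In the event that the AI-ECG detects cardiomyopathy (and baseline echocardiogram showed normal ejection fraction), this would trigger an echocardiogram". The only other protocol echo is the end-of-participation repeat in women with detected cardiomyopathy.

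On entry time, section 3.1 says "Patients can enter the study at any time point (Fig 6) during pregnancy or the postpartum period", and section 3.3 allows "a maximum of 7 visits (at pre-specified time points) depending on the time they enter the study".

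**The concern.** At baseline every intervention-arm woman is verified by echo whatever her AI-ECG shows. At follow-up only AI-positives are verified. A triggered pair is therefore a true positive or a false positive; it cannot be a false negative or a true negative. Pooling such pairs with baseline pairs adds to the false-positive count and never to the true-negative count.

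The clause on differential follow-up testing suggests that follow-up pairs may enter the accuracy measures: with baseline pairs alone there would be no differential testing to account for. The remedy it offers does not work as a correction on either reading of study entry:

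- **Time of enrolment**, the reading that fits sections 3.1 and 3.3. Every stratum with follow-up visits still mixes fully verified and positives-only pairs. The bias grows with the number of visits, so strata would differ even if true accuracy were the same.
- **Baseline versus follow-up.** The baseline stratum is sound, but the triggered stratum has sensitivity 100% and specificity 0% by construction.

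At stake are the descriptive accuracy results in 7.3.1 and the secondary ones in 7.3.3, including performance by postpartum status. With one ECG per window in section 3.1, entry in pregnancy allows 4 to 6 further screens and postpartum entry 0 to 3, study end permitting. A specificity difference by postpartum status could arise from that count alone.

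**Working it through.** **The plan's own figures.** The plan states no sensitivity or specificity target. The prevalence used here, 4%, is the AI-ECG arm rate in section 7.1. The calculation it supports there reproduces: [1.960·√(2·0.025·0.975) + 0.842·√(0.01·0.99 + 0.04·0.96)]² / 0.03² = 424 per group, as stated.

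**Inputs.** From the documents: 1,200 accrued at 1:1, so 600 in the intervention arm; 4% prevalence, so 24 cases and 576 non-cases; 0 to 6 follow-up screens. Assumed: true sensitivity 80%, true specificity 90%, new disease in 1% of baseline-normal women (range 0.5% to 2%), one triggered echo per triggered woman.

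**Baseline pairs only.** TP 19.2, FN 4.8, FP 57.6, TN 518.4. The 95% Wilson interval for specificity (518/576) is 87.2% to 92.1%; for sensitivity (19/24) it is 59.5% to 90.8%.

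**Adding triggered pairs.** New true positives: 576 × 0.01 × 0.8 = 4.6. The other triggered women are false positives. Pooled specificity = 518.4 / (576 + added FP).

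| Triggered | Women | Added FP | Specificity | AUC |
|---|---|---|---|---|
| none | 0 | 0 | 90.0% | 0.933 |
| 2.5% | 14.4 | 9.8 | 518.4/585.8 = 88.5% | 0.936 |
| 5% | 28.8 | 24.2 | 518.4/600.2 = 86.4% | 0.930 |
| 10% | 57.6 | 53.0 | 518.4/629.0 = 82.4% | 0.917 |
| 20% | 115.2 | 110.6 | 518.4/686.6 = 75.5% | 0.896 |

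The AUC column uses an equal-variance binormal model (separation 2.123), with triggered scores drawn from above the threshold. At 5% triggered, AUC is 0.925 with 0.5% new disease and 0.938 with 2%, so its direction is not fixed.

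Specificity leaves the baseline Wilson interval when 518.4/0.872 − 576 = 18.5 false positives have been added. With the 4.6 true positives that is 23.1 women, or 4.0% triggered (3.6% and 4.8% for 0.5% and 2% new disease).

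Pooled sensitivity = (19.2 + 4.6)/(24 + 4.6) = 83.2% (81.8% to 85.5% over the same range). The shift is small beside its interval.

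**Plausible trigger rates.** Assume exchangeable normal scores with 90% specificity at each visit, full attendance, and within-woman correlation 0.9 to 0.5. Let f be the chance that a disease-free woman is AI-negative at baseline and positive at one or more of k later screens. Apparent specificity = 0.90/(1 + f).

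| k | f | Apparent specificity |
|---|---|---|
| 0 | 0 | 90% |
| 1 | 3.1% to 6.8% | 87.3% to 84.3% |
| 3 | 6.3% to 15.9% | 84.6% to 77.7% |
| 6 | 8.9% to 24.5% | 82.6% to 72.3% |

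A beta-binomial model with correlation 0.3 gives the same pattern: 84.7%, 78.8% and 74.2% for k = 1, 3 and 6. By time of entry that is 74.2% for the first trimester, 78.8% for 0 to 6 weeks postpartum and 90.0% for 5 to 12 months, with true specificity 90% throughout.

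If any later positive counts as a trigger, and not only a newly positive one, f is 10.0% at k = 1 and 18.2% to 32.1% at k = 6.

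**Another pairing.** Score the baseline AI result against LVEF below 50% at any time, with the 4.6 later cases AI-negative at baseline. Sensitivity becomes 19.2/28.6 = 67.1% and specificity 513.8/571.4 = 89.9%. The direction of bias therefore depends on a pairing the plan does not state.

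**The case against.** The strongest reply is that the reference standard is stated. The Study Summary names baseline echoes, nothing in 7.3.1 or 7.3.3 contradicts it, and no section says that triggered echoes will be pooled. If the Summary governs, the bias does not arise. On the baseline-versus-follow-up reading, the stratification would separate sound pairs from selected ones. Section 7.4.5 promises a detailed SAP where pairing can be settled, and the STARD reporting promised in 7.3.3 would show denominators, so pooling might be noticed.

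Part of this stands. The point is a gap in specification, not a proven error. But the Summary does not close it. The clause in 7.3.1 presupposes follow-up testing that affects the accuracy measures, and 7.3.3 takes in all protocol echoes. Even on the favourable reading one stratum is uninformative. The promised SAP is where to fix the point, and visible denominators would reveal the bias without removing it.

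On size, accuracy, new disease, correlation and attendance are all assumed. The 72% figure needs the lowest correlation, six follow-up visits and full attendance, while section 7.1 expects withdrawals and no-shows. Visit counts are potential, since follow-up ends at study end. The AUC model ignores that newly positive women were AI-negative at baseline, so its third decimal should not be relied on. AUC is also the only metric 7.3.3 names explicitly, and it moves less than specificity. These points limit the size, not the direction for specificity.

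**Conclusion.** The concern holds, conditionally: if triggered pairs are pooled, specificity is biased down whenever any triggered woman is disease-free. That direction is algebraic. The amount rests on the assumptions above: about 1.5 to 14.5 percentage points for trigger rates of 2.5% to 20%, and outside the baseline confidence interval above roughly a 4% trigger rate. Sensitivity rises by about 2 to 5 points, and AUC can move either way.

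Stratifying by study entry does not correct this on the enrolment-time reading. On the other reading it yields one sound stratum and one with no information about accuracy. The plan could therefore report specificity several points too low while saying that differential testing had been accounted for.

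The primary chi-square comparison and its sample size are unaffected. The change should be made before analysis; confidence is medium because the documents do not say how the pairs will be formed.

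**What to change.** In 7.3.1, 7.3.3 and the SAP announced in 7.4.5:

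- State that AUC, sensitivity and specificity, overall, by subgroup and by LVEF cut-off, use only the baseline 12-lead ECG paired with the baseline echo, one pair per woman, in line with the Study Summary.
- Report triggered follow-up echoes separately, as the proportion newly AI-positive and the yield or positive predictive value. Keep recovery echoes out of the accuracy set.
- Define study entry, and keep stratification by it as description only, not as a correction for differential testing.
- Reconcile the trigger wording. Section 3.1 refers to a newly positive screen; sections 5.1 and 6.3 read as any later positive after a normal baseline echo. The yield denominator depends on which applies.

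The cost is wording only, since all the data are already planned. The downside is that cases first found at follow-up (about 5 in the illustration) leave the accuracy set and appear in the yield table instead.

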7.4. Additional Statistical Considerations

7.4.1. Handling of Missing Data

Missing data may occur throughout the study. The primary analysis, which is based on the AI-ECG prediction for cardiomyopathy is expected to be calculated once digital is received. In the event that the digital ECG file is missing or corrupted, attempts will be made to re-record the ECG. In order to ensure that these repeated ECGs are obtained in a timely fashion, ECGs will be reviewed at the local sites daily and will be transmitted to the coordinating center at Mayo Clinic at the end of every week for additional review. For demographic and medical history data, any missing data will be reported as such in the final analysis.

7.4.2. Multiplicity

There will be no adjustment to the level of significance for multiple testing. All results will be reported unadjusted at the alpha=0.05 level of significance using estimates and 95% confidence intervals.

7.4.3. Interim Analysis

There is no planned interim analysis.

7.4.4. Analysis Sets

The analysis set for this study will follow the modified intention to treat principle. To be included in the analysis, the participant needs to be randomized and complete at least the baseline assessments and testing.

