6.1. Schedule of Events

6.1.1 - Control Arm

Assessment	Screening	Baseline, Randomization Visit 1	Visits 2 -7
------------	-----------	---------------------------------------	-------------

Inclusion/Exclusion Criteria	X	X	
Informed Consent ^a		X	
Demographics		X	
Clinical Assessments ^b		X	X
Medical History		X	
New Clinical Diagnosis			X
Current Medications		X	
Blood Chemistries ^c		X	
Hematology ^d		X	
Urine Analysis ^e		X	X
Inclusion/Exclusion Criteria	X	X	
Enrollment/Randomization		X	
12 lead ECG		X	X
AI-ECG – Sex and Age Determination		X	X

^aConsent may be obtained prior to baseline/randomization visit^bHeight, weight, blood pressure and heart rate^cTo be abstracted from medical records – Serum Cr, eGFR^dTo be abstracted from medical records – Hemoglobin (g/dl) or Hematocrit (%) or Packed Cell Volume; Hemoglobin Genotype (Hb AA, AS, SS, Sc); Rhesus factor (negative or positive), infectious screen.^eTo be abstracted from medical records – Positive for proteins (Yes or No)

6.1.2 - Intervention Arm

Assessment	Screening	Baseline, Randomization Visit 1	Visits 2-7
Inclusion/Exclusion Criteria	X	X	
Informed Consent ^a		X	
Demographics		X	
Clinical Assessments ^b		X	X
Medical History		X	
New Clinical Diagnosis			X
Current Medications		X	
Blood Chemistries ^c		X	
Hematology ^d		X	
Urine Analysis ^e		X	X
Enrollment/Randomization		X	
12 lead ECG		X	X
AI-ECG - Sex, Age, and Cardiomyopathy Determination		X	X
Portable ECG ^f		X	X
Echocardiogram ^g *		X	

^aConsent may be obtained prior to baseline/randomization visit^bHeight, weight, blood pressure and heart rate^cTo be abstracted from medical records – Serum Cr, eGFR^dTo be abstracted from medical records – Hemoglobin (g/dl) or Hematocrit (%) or Packed Cell Volume; Hemoglobin Genotype (Hb AA, AS, SS, Sc); Rhesus factor (negative or positive), infectious screen.^eTo be abstracted from medical records – Positive for proteins (Yes or No)^fPortable ECGs will be performed only among those in the intervention arm

^gEchocardiograms will be performed on all participants in the intervention arm at baseline and *if any new subsequent ECGs flag positive based on the AI-ECG predictions for cardiomyopathy (low ejection fraction) provided the baseline echocardiogram was normal. Participants with cardiomyopathy detected at any time point during the study will have a repeat echocardiogram at the end of study participation or 12 months postpartum (whichever is earlier) to assess for left ventricular recovery.

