6.2.2. Randomization/Baseline visit

After informed consent has been obtained, the following procedures will be completed per the schedule of events table:

Control Arm

- Enrollment Randomization
- Demographic information
- Clinical Assessments
- Medical history
- Current Medications
- Blood Chemistries
- Hematology
- Urine Analysis
- 12-lead ECG
- AI-ECG Sex & Age Determination

Intervention Arm

- Enrollment Randomization
- Demographic information
- Clinical Assessments
- Medical history
- Current Medications
- Blood Chemistries
- Hematology
- Urine Analysis
- 12-lead ECG
- AI-ECG Sex, Age, & Cardiomyopathy Determination
- Portable ECGs
- Echocardiogram(s)

Visits 2-7**Control Arm**

- New Clinical Diagnosis
- Clinical Assessments
- Current Medications
- Urine Analysis
- 12-lead ECG
- AI-ECG Sex & Age Determination

Intervention Arm

- New Clinical Diagnosis
- Clinical Assessments
- Urine Analysis
- 12-lead ECG
- AI-ECG Sex, Age, & Cardiomyopathy Determination
- Portable ECGs

- Repeat echocardiogram for Positive AI-ECG screen/new cardiomyopathy diagnosis (if baseline echocardiogram was normal)

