7.1. Sample Size Determination

LVEF<50% is not expected to be diagnosed in the control arm due to the lack of routine echocardiograms, but for sample size calculations, we have assumed that 1% will be diagnosed based on literature derived incidence rate of 1 in 100 deliveries (M. B. Davis et al., 2020). With the AI-ECG screening, we hypothesize that an increase in the number of cases will be detected. For sample size estimation consideration, an unpublished, ongoing pilot study conducted in the US estimates the prevalence as 5.3% (3/57) for <=35% and 7% (4/57) for <50%. Sample size estimation is based on a conservative estimate of 4% in the AI-ECG arm. At the alpha=0.05 and 80% power, the sample size is estimated to be 424/group. For the secondary composite endpoint, approximately 5% of the sample is expected to experience hypertensive disorders (Ying, Catov, & Ouyang, 2018). We hypothesize that the addition of AI-ECG will increase the detection of cardiomyopathies and other structural defects of the heart. Accordingly, we assume composite event rates of 5% vs. 10% for the control vs. AI-ECG arm. At 80% power and alpha=0.05, a sample size of 434/group is required. For the final sample size, these estimates are rounded up to 500/group (1000 total) to account for the uncertainties in the calculations. Due to the variability in the occurrence of cardiomyopathy across sites, need to account for study participant withdrawal from the study, no-shows to study visits, and loss to follow up, we plan to enroll 1,400 patients to achieve an accrual target of 1,200 participants while ensuring balanced accrual across all 6 sites.

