7.2. Study Endpoints

7.2.1. Primary Study Endpoints

The primary study endpoint will be left ventricular ejection fraction (LVEF) <50% diagnosed by echocardiography during pregnancy or within 12 months postpartum

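### Section 7.4.4 does not limit the baseline testing needed for inclusion to procedures both arms have; on one natural reading it drops intervention women who miss the echocardiogram

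*Combined protocol and SAP*

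**What the plan says.** Section 7.4.4 adopts a modified intention-to-treat set and gives one rule: "To be included in the analysis, the participant needs to be randomized and complete at least the baseline assessments and testing". No list of procedures follows, and there is no distinction by arm.

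The baseline procedures differ by arm. Section 3.1 says "Only participants in the intervention arm will have a baseline echocardiogram as well as simultaneous portable ECGs recorded". Footnote g of the intervention schedule (Section 6.1.2) says echocardiograms "will be performed on all participants in the intervention arm at baseline". The Section 6.2.2 list for the intervention arm adds the AI-ECG cardiomyopathy determination, the portable ECGs and the echocardiogram. The control list ends with the 12-lead ECG and the age and sex estimate.

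The primary endpoint (Section 7.2.1) is LVEF below 50% "diagnosed by echocardiography during pregnancy or within 12 months postpartum". Section 7.3.2 compares the proportions with a documented finding, using a two-sided chi-square test at 0.05 without continuity correction. Within the set, therefore, no documented finding already counts as a non-event. What is unclear is who belongs to the set.

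**The concern.** If the echocardiogram is part of baseline testing, inclusion depends on a procedure that follows randomisation, exists in one arm only and is how the primary endpoint is found. An intervention woman without an echocardiogram leaves the denominator; a control without one remains as a non-event. Failure to obtain an echocardiogram is part of how the screening strategy performs, and the primary comparison would leave it out.

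Other sections do not settle the matter:

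- **Section 7.4.1** reports missing demographic and history data as missing, so not every baseline item can be compulsory, but it does not mention a missing echocardiogram.
- **Section 7.3.1** tabulates outcomes for all enrolled women and by randomised group, but only descriptively.
- **Section 7.4.5** promises a detailed SAP; the present text does not itemise the set.

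**Working it through.** **Inputs from Section 7.1.** Control detection is 1%. For the intervention, "Sample size estimation is based on a conservative estimate of 4% in the AI-ECG arm". The accrual target of 1,200 at 1:1 gives 600 per arm.

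**Assumptions.** m is the share of intervention women who miss the baseline echocardiogram: 5%, 10% or 20%. u is the share of those women later documented with LVEF below 50%. The documents give neither.

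**The plan's own figure.** n = [1.96√(2×0.025×0.975) + 0.842√(0.01×0.99 + 0.04×0.96)]² / 0.03² = 423.97, so 424 per group, as Section 7.1 states. The concern does not affect it.

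**Reading A: 4% is the rate among echoed women.** The echo-required set shows 4% − 1% = 3.0 points. The all-randomised rate is (1−m)×4% + m×u, and the overstatement is 3.0/(rate − 1%) − 1. For m = 10% and u = 0 the rate is 0.90×4% = 3.6%, the difference 2.6 points, and 3.0/2.6 − 1 = 15.4%.

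All-randomised difference in points (overstatement by the echo-required set):

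| m | u = 0 | u = 1% | u = 2% | u = 3% | u = 4% |
|---|---|---|---|---|---|
| 5% | 2.80 (7.1%) | 2.85 (5.3%) | 2.90 (3.4%) | 2.95 (1.7%) | 3.00 (0) |
| 10% | 2.60 (15.4%) | 2.70 (11.1%) | 2.80 (7.1%) | 2.90 (3.4%) | 3.00 (0) |
| 20% | 2.20 (36.4%) | 2.40 (25.0%) | 2.60 (15.4%) | 2.80 (7.1%) | 3.00 (0) |

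Above u = 4% the sign reverses: with m = 10% and u = 8% the all-randomised difference is 3.4 points against 3.0.

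**Reading B: 4% is the rate for the whole arm, as Section 7.1 words it.** The all-randomised difference is 3.0 points. The echoed rate is (4% − m×u)/(1−m). For u = 0 to 1% the restricted difference is 3.21-3.16, 3.44-3.33 or 4.00-3.75 points, overstated by 7.0-5.3%, 14.8-11.1% or 33.3-25.0%.

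**What u depends on.** Sections 3.1 and 6.2 say a newly positive AI-ECG triggers an echocardiogram in the intervention arm and state no further condition. Sections 5.1, 6.1.2 (footnote g), 6.2.2 and 6.3 add that the baseline echocardiogram was normal. If that condition applies, a woman with no baseline echocardiogram has no clear route to a triggered one and u is likely to be low; if it does not, u could be higher. These sections must be reconciled.

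**Against sampling error.** The standard error of the difference at 600 per arm is √(0.04×0.96/600 + 0.01×0.99/600) = 0.90 points. The shift under A is m×(4% − u): for u = 0 to 1%, 0.20-0.15, 0.40-0.30 or 0.80-0.60 points, all below one standard error. Under B the extreme case (m = 20%, u = 0) is 1.0 point, about one standard error.

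**Type I error** (exact, 1% in both arms, 600 randomised per arm). Dropping only undetected intervention women gives 5.3%, 5.1% or 6.9% for 5%, 10% or 20% dropped. The same group sizes without selective dropping give 5.1%, 4.6% or 4.7%; with none dropped it is 4.3%.

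**The case against.** The strongest objection is to the reading. The heading of Section 5 attaches testing to the ECG and names the echocardiogram separately. On that usage, baseline testing is the 12-lead ECG that both arms have, and the arm-specific exclusion disappears. This stands as a rival reading but is not decisive: Section 7.3.1 uses the word for follow-up that probably includes echocardiography, and Section 6.1.2 places the echocardiogram among the baseline procedures.

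Second, 0-1% later detection is a pessimistic range. Women who miss the baseline echocardiogram but stay in the study still have AI-ECG screening, with up to seven ECGs in all. At 2-3% detected the bias is about 2-3%, 3-7% or 7-15% under A, roughly half or less. This stands, and both ranges belong in the conclusion.

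Third, the shift is small against sampling error and would be partly visible. Section 7.3.1 shows outcomes for all enrolled women, Section 8.3 requires missing data to be explained, and Section 9.1 checks that missing examinations are indicated. This lowers the weight of the point. It does not decide which women enter the primary test.

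Fourth, limiting the rule to common procedures would cure the ambiguity without replacing the modified set. That is fair, and it is offered below as an alternative.

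**Conclusion.** The point holds as an unsettled rule that should be corrected: one natural reading makes inclusion in the primary test depend on an outcome-ascertaining procedure that only one arm undergoes. On that reading, with the assumed 5%, 10% or 20% missed and 4% taken as the echoed-women rate, the overstatement is about 5-7%, 11-15% or 25-36% at 0-1% later detection and about 2-3%, 3-7% or 7-15% at 2-3%. It is zero at equal detection and reverses above that. The effect on false positives is small unless many women are dropped.

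A reader might infer more than the documents support:

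- **That the plan does exclude these women, or that its result will be inflated.** The rival reading is open, and neither the missed-echo rate nor later detection is known.
- **That the gap between 1,400 and 1,200 is a missed-echo rate.** Section 7.1 gives it several causes, beginning "Due to the variability in the occurrence of cardiomyopathy across sites, need to account for study participant withdrawal from the study", and does not split it by cause or arm.
- **That correcting the set makes ascertainment equal.** Section 7.1 itself says "LVEF<50% is not expected to be diagnosed in the control arm due to the lack of routine echocardiograms". That larger design feature is separate and would remain.

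**What to change.** In Section 7.4.4, make all randomised women, as assigned, the set for the primary chi-square test, with no documented LVEF below 50% counted as not detected, as Section 7.3.2 implies. If a modified set is kept, define it only by baseline procedures common to both arms, such as the 12-lead ECG. Keep the echo-completed set, with its procedures itemised, as a sensitivity analysis. Report exclusions and baseline echocardiogram completion by arm, with reasons. Reconcile the sections on when a positive AI-ECG triggers an echocardiogram.

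The change is wording only and needs no new data. Exact power of the uncorrected test at 600 per arm, with 0-1% later detected:

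| Missed | A: all randomised | A: echo-required | B: all randomised | B: echo-required |
|---|---|---|---|---|
| 5% | 91-92% | 93% | 94% | about 95% |
| 10% | 88-90% | 93% | 94% | 96-97% |
| 20% | 79-84% | 92% | 94% | about 98% |

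A normal approximation gives somewhat lower values under A (all randomised 89-90%, 85-87% and 76-81%; echo-required 91%, 90% and 89%) in the same order. If all 1,400 enrolled women are randomised (700 per arm, an assumption), the all-randomised figure under A with 20% missed is 85-89%. The higher power of the echo-required set under A comes from setting aside women in whom the strategy was not completed, so it is not a reason to prefer that set.
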